4.3.2 Dosing Rules (30 - 100 mg/kg) (Q3W, Part II)

Sentinel dosing will be applied for 30-100mg/kg dosing. The second subject on a particular dose level can receive the first dose only after the first subject has been followed up for 28 days (additional precaution compared to traditional 3+3 model) after the first dose, and has not demonstrated any DLT. The third subject may receive the first dose after the second subject has been followed up for 28 days after the first dose and and neither of the subjects have demonstrated any DLTs. DLT evaluable subject will have at least one dose of IMP and have at least 28 days of follow-up after IMP infusion. If these criteria are not met, the subject will be replaced. Once three evaluable subjects have received at least one dose and have been followed up at for 28 days with no DLTs, all remaining subjects on the dose level may be enrolled without any hold. If any of the first three subjects cannot be followed for the full 28-day DLT observation period for reasons other than DLT, the subject may be replaced in order to obtain the required tolerability information of 28 days from the first IMP infusion, before the remaining subjects on the dose level may be enrolled. The replaced subject will, however, count towards the cohort of 10 subjects. The same rules will apply for the other dose levels.

5 ELIGIBILITY

Subjects registered onto this trial must fulfil all the common inclusion and exclusion criteria and fulfil their disease specific inclusion and exclusion criteria.

5.1 Inclusion and Exclusion Criteria

5.1.1 Inclusion Criteria

Subjects must meet all of the following inclusion criteria to be eligible for participation in the clinical trial:

- 1) Written Informed Consent
- 2) Aged \geq 18 years male or female
- 3) Tumour sample should be collected during screening period. If a recent tumour biopsy obtained within six months before the date of consent is available (or older, as agreed on a case by case basis with the sponsor), that may be used. At the discretion of the sponsor, the tumour sample may be optional for certain subjects in Part III
- 4) Life expectancy $>$ 12 weeks
- 5) Histologically confirmed advanced (inoperable or metastatic) malignancies in which (according to the view of the investigator) no curative, effective or suitable treatment options exist.
 - Hepatocellular carcinoma
 - Gallbladder cancer or intra- or extrahepatic cholangiocarcinoma
 - Colorectal adenocarcinoma
 - Serous poorly differentiated (Grade 3) ovarian adenocarcinoma or undifferentiated ovarian cancer
 - Pancreatic ductal adenocarcinoma
 - Immunotherapy (IO) resistant cutaneous melanoma (progression during programmed cell death protein-1 (PD-1)/programmed cell death ligand-1 (PD-L1) or CTLA-4 antibody therapy)
 - Uveal melanoma in Parts II and III
 - Gastric adenocarcinoma (including adenocarcinoma of the distal esophagus / GE junction) in Parts II and III
 - ER+ breast cancer in Parts II and III
 - Anaplastic thyroid cancer in Parts II and III
- 6) Eastern Cooperative Oncology Group (ECOG) performance status 0 or 1
- 7) Measurable disease in Parts II and III
- 8) Adequate bone marrow, liver and kidney function defined as

Blood white blood cell \geq lower limit of normal

Blood neutrophil count $\geq 1 \times 10^9/L$

Blood platelet count $\geq 100 \times 10^9/L$, for HCC $\geq 50 \times 10^9/L$

Blood haemoglobin $\geq 9.0 \text{ g/dL}$

Creatinine clearance $> 40 \text{ mL/min}$ calculated by Cockcroft-Gault formula

AST $\leq 3 \times \text{ULN}$ ($\leq 5 \times \text{ULN}$ when HCC or hepatic metastases are present)

ALT $\leq 3 \times \text{ULN}$ ($\leq 5 \times \text{ULN}$ when HCC or hepatic metastases present)

Bilirubin $\leq 1.5 \times \text{ULN}$

Albumin $\geq 3.0 \text{ g/dL}$

The most recent measurements taken during the screening period must be within the required limits for the patient to be considered eligible (i.e. criteria met once during the screening period are not sufficient if there are more recent measurements available that are not within the required limits. It is however acceptable to repeat measurements if the initial measurements or subsequent measurements taken during the screening period are not within the required limits; the patient is eligible providing that the newest measurements are within the required limits). However, once a subject is out of the screening period, and has had eligibility confirmed and

been enrolled, the pre-dose laboratory assessments are not subjected to inclusion criteria limits, but only for investigators assessment of subject safety.

- 9) Women of child-bearing potential must have a negative pregnancy test in serum prior to trial entry
- 10) Women of child-bearing potential and men who have partners of child-bearing potential must be willing to practise highly effective contraception for the duration of the trial and for three months after the completion of treatment

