3.10 Outcome Measures

Part I

Primary outcome measure

- Tolerable dose(s) will be determined by the TITE-CRM based on the occurrence/non-occurrence of dose limiting toxicities in the trial subjects according to definitions in [Section 4.1](#).

Secondary outcome measures

- The PK profile of a single dose (during Cycle 1) and repeated doses (during Cycles 1-5) of FP-1305 will be determined by repeated measurements of the drug concentration in the circulation. Peak concentration (C_{max}), trough concentration (C_{min}), AUC, clearance, volume of distribution, and terminal half-life (t_{1/2}) for each dose level will be determined.
- Immunogenicity will be evaluated by assessing anti-drug antibodies in the circulation periodically during treatment and follow-up.

- The ORR to the treatment will be determined by tumour imaging according to RECIST 1.1. The CBR is the proportion of subjects that have a complete response, partial response, or stable disease. The irORR will also be calculated.

Exploratory outcome measures

- CLEVER-1 on circulating monocytes will be determined by flow cytometry. The proportion of circulating CD14+ monocytes binding labelled FP-1305 prior to treatment and their mean fluorescence intensity (MFI) will be used to define CLEVER-1 positivity. CLEVER-1 in tumour samples (if available) prior to treatment will be identified with immunohistochemistry and reported as positive cells / mm² of sample. The MFI of CLEVER-1 positive cells will be correlated to the number of CLEVER-1 positive cells in the tumour sample if the number is available.
- The proportion of circulating monocytes binding labelled FP-1305 and another CLEVER-1 binding antibody prior to and during the treatment at selected time points and their MFI will be reported.
- Potential predictive genetic, cellular and other markers will be associated with FP-1305 clinical activity as determined by ORR and irORR. This includes but is not limited to the correlation of response and immune cell profile, cytokine/chemokine profile and the proportion of CLEVER-1-positive monocytes, CD4, CD8, their ratio and regulatory T-cells in the circulation and in tumour specimens prior to treatment and in circulation during the first cycle of treatment.

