15.1 Trial Population

The trial subject population includes subjects who have advanced (inoperable or metastatic) cutaneous melanoma, pancreatic ductal adenocarcinoma, ovarian cancer, colorectal adenocarcinoma, hepatocellular carcinoma, gallbladder cancer, cholangio-carcinoma, uveal melanoma, gastric (including GE junction) adenocarcinoma, ER+ breast cancer and anaplastic thyroid cancer without standard treatment options available and who adhere to the trial inclusion and exclusion criteria.

For the purpose of analyses the following populations are defined:

Safety population: Includes all subjects who have received any amount of FP-1305

DLT evaluable population: Includes all subjects in Part I who have received at least one dose of FP-1305 and followed up for at least three weeks. Any subject that withdraws, discontinues from the trial or dies not related to treatment prior to the end of the 9-week DLT assessment period will be replaced.

Efficacy evaluable population: Includes all subjects who have received at least one dose of FP-1305 for the first time and has tumour imaging conducted at the baseline, and at least once during the treatment or progress or die due to their disease before the first tumour imaging post FP-1305 administration.

Subjects that re-initiate the treatment: Includes all subjects that have received at least one dose of FP-1305 after re-initiation of the therapy and has tumour imaging conducted at the baseline, and at least once during the treatment or progress or die due to their disease before the first tumour imaging post FP-1305 administration will be analysed for efficacy after the re-initiation in a separate cohort.

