15.6 Planned Main Analyses

Part I

The main analysis for determining the recommended dose to be expanded upon will take place once all subjects in part I have been recruited to trial and have been followed-up for the 9-week DLT assessment period.

Part II

Each cohort will be analysed when ten evaluable subjects have been accrued and treated with the selected dose. Subjects from Part I can be included into the cohort of ten subjects if they have been treated with the selected dose.

Part III

Each cohort that is continued after the analysis of Part II will be analysed when 29 evaluable subjects have been accrued and treated with optimal dose or until the required 4 responders are reached. The cohort can continue accruing subjects if the stopping rule is not met. The final analysis of each cohort is when the particular cohort has been considered complete.

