22 APPENDIX 1 - RECIST CRITERIA

The following contains excerpts from the RECIST version 1.1 plus trial specific instructions.

A free copy of the revised guidelines is available from <https://recist.eortc.org/recist-1-1-2/>

<http://www.eortc.be/recist/default.htm>

(Eisenhauer *et al.*, 2009)

Measurability of Tumour Lesions at Baseline

Only patients with measurable disease at baseline should be included in Parts II and III. Measurable disease is defined by the presence of at least one measurable lesion. At baseline, tumour lesions will be categorised as follows:

- Measurable
- Non-measurable

Measurable lesions are those that can be accurately measured in at least one dimension (longest diameter to be recorded) with a minimum size of 10 mm by CT scan (CT scan slice thickness no greater than 5 mm), 10 mm caliper measurement by clinical exam (lesions which cannot be accurately measured with callipers should be recorded as non-measurable) and 20 mm by chest X-ray. For malignant lymph nodes to be considered pathologically enlarged and measurable, a lymph node must be ≥ 15 mm in short axis when assessed by a CT scan (at baseline and during treatment, only the short axis will be measured and followed).

Non-measurable lesions are all other lesions, including small lesions (longest diameter <10 mm or pathological lymph nodes with ≥ 10 to >15 mm short axis) and truly non-measurable lesions.

Lesions considered to be truly non-measurable include the following: bone lesions, leptomeningeal disease, ascites, pleural/pericardial effusion, inflammatory breast disease, lymphangitis cutis/pulmonis, abdominal masses that are not confirmed and followed by imaging techniques, and cystic lesions.

Tumour lesions that are situated in a previously irradiated area are not considered measurable. The term "evaluable" in reference to measurability is not recommended and will not be used because it does not provide additional meaning or accuracy.

All measurements should be recorded in metric notation using callipers (or a ruler) if clinically assessed. All baseline evaluations should be performed as closely as possible to the beginning of treatment and never more than 4 weeks before the beginning of treatment.

Specifications by Methods of Measurements

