12.1.1 Efficacy variable

The ORR to the treatment will be determined by tumour imaging according to RECIST 1.1 (as specified in study protocol). Proportion of patients responding to treatment (including Partial, Complete responses) will be summarised by dose (and disease type).

The CBR is the proportion of subjects that have a complete response, partial response, or stable disease. The irORR will also be calculated.

Potential predictive genetic, cellular and other markers will be associated with FP-1305 clinical activity as determined by ORR and irORR. This includes but is not limited to the correlation of response and immune cell profile, cytokine/chemokine profile and the proportion of CLEVER-1-positive monocytes, CD4, CD8, their ratio and regulatory T-cells in the circulation and in tumour specimens prior to treatment and in circulation during the first cycle of treatment.

13 PK variables

The PK profile of a single dose (during Cycle 1) and repeated doses (during Cycles 1-5) of FP-1305 will be determined by repeated measurements of the drug concentration in the circulation. Peak concentration (C_{max}), trough concentration (C_{min}), area under the plasma concentration versus time curve (AUC), clearance, volume of distribution, and terminal halflife ($t_{1/2}$) for each dose level will be determined.

14 Other variables

Immunogenicity will be evaluated by assessing anti-drug antibodies in the circulation periodically during treatment and follow-up.

CLEVER-1 on circulating monocytes will be determined by flow cytometry. The proportion of circulating CD14+ monocytes binding labelled FP-1305 prior to treatment and their mean fluorescence intensity (MFI) will be used to define CLEVER-1 positivity. CLEVER-1 in tumour samples (if available) prior to treatment will be identified with immunohistochemistry and reported as positive cells / mm^2 of sample. The MFI of CLEVER-1 positive cells will be correlated to the number of CLEVER-1 positive cells in the tumour sample if the number is available.

The proportion of circulating monocytes binding labelled FP-1305 and another CLEVER-1 binding antibody prior to and during the treatment at selected time points and their mean fluorescence intensity will be reported.

15 Analysis of safety and tolerability

All subjects in the FAS-S analysis set (all patients receiving study treatment) will be included in the safety and tolerability analysis.

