Regarding Part II, the first three subjects recruited to the unique cohort are included in the DLT evaluable population. The amount is expanded to six subjects if there is one DLT event in the first three subjects. The following cohorts are investigated: Q3W cohorts at dose levels that have not previously been tested in Part I, Q2W cohorts at each new dose level and Q1W cohorts at each new dose level. DLT assessment period in Part II is 4 weeks from the first dose of FP-1305.

Efficacy evaluable population: Includes all subjects who have received at least one dose of FP-1305 for the first time and has tumour imaging conducted at the baseline, and at least once during the treatment or progress or die due to their disease before the first tumour imaging post FP-1305 administration. This formulates the Full Analysis Set for Efficacy (FAS-E).

In the FAS populations also Part I subjects will be included.

9 General statistical considerations

Summary statistics will include at least the number of subjects, mean, standard deviation, median, minimum and maximum for continuous variables, and frequencies and percentages for categorical variables. All data collected will be listed by subject.

In Part II, the disease group or dosing cohorts of 10 subjects will be presented separately as also the Simon's design rule will be applied separately for each cohort. In addition, the cohorts using originally recommended dosing regimen for Part II, Q3W (1.0 mg for all cohorts and 0.3 mg/kg and 3.0 mg/kg for colorectal adenocarcinoma), will form a population (originally enrolled part II cohorts). Also, a pooled population of Part I subjects (n=30) and Part II originally enrolled subjects (n=120) will be used for survival endpoints. The total number of subjects in this dataset is n=148 as there were 2 part I subjects (colorectal adenocarcinoma 0.3 mg/kg) included in Part II.

In the statistical analyses a p-value less than 0.05 will be considered as an indication of statistical significance. If not stated otherwise, all tests will be performed as two-sided tests and two-sided 95% confidence intervals will be produced. Missing values will not be imputed in the analyses.

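### Protocol 15.6 admits Part I subjects to a Part II cohort on dose alone, without Part II's measurable-disease condition, and a non-progressing subject without target lesions has no defined overall response

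*Protocol*

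**What the plan says.** **Eligibility.** Protocol 5.1.1, criterion 7, is "Measurable disease in Parts II and III". Appendix 1 repeats it: "Only patients with measurable disease at baseline should be included in Parts II and III". Part I has no such criterion.

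**Part I scoring.** Part I subjects are still scored for response. Protocol 3.10 lists among the Part I secondary outcomes "The ORR to the treatment will be determined by tumour imaging according to RECIST 1.1". The Part I SAP, section 12.1.1, plans "Proportion of patients responding to treatment (including Partial, Complete responses) will be summarised by dose (and disease type"), and its section 12 puts ORR first in the hierarchy of key efficacy response variables.

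**Carry-over.** Protocol 15.6 says "Subjects from Part I can be included into the cohort of ten subjects if they have been treated with the selected dose". No other condition is given. The Part II SAP, section 9, records that this was used: "there were 2 part I subjects (colorectal adenocarcinoma 0.3 mg/kg) included in Part II".

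**Efficacy population.** Protocol 15.1 admits a dosed subject who "has tumour imaging conducted at the baseline, and at least once during the treatment", or who progresses or dies of the disease before the first on-treatment image. Measurable disease is not mentioned. Both SAPs adopt this definition, and the Part II SAP (section 8) adds that Part I subjects belong to its full analysis sets.

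**Gate.** Protocol 15.7 and Part II SAP 12.1 require clinical benefit (CR, PR or SD) in at least 1 of 10 subjects before a cohort may go to Part III.

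**The concern.** Part II ORR, CBR and irORR are primary outcomes, and each cohort has only ten subjects. If one of the ten came from Part I without a target lesion, two things follow.

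First, that subject cannot reach PR. In Appendix 1, PR requires either a 30% fall in the target-lesion sum or a target-lesion CR with other disease remaining. The subject then sits in the ORR denominator with little chance of entering the numerator.

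Second, the plan does not say how to score the subject if the disease does not progress. Table B of Appendix 1 gives persisting non-target lesions a combined label of incomplete response and stable disease. Someone filling in the response form could take that as overall SD, and one SD is enough to meet the 1/10 rule. The same CBR call also sorts subjects into DCR and non-DCR for the Part II biomarker analyses (Part II SAP 12.1 and 12.3).

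**Working it through.** **1. Was there a carry-over?** The Part II SAP gives 30 Part I subjects, 120 in the originally enrolled Part II cohorts (12 cohorts of ten), and 148 in the pooled set. 30 + 120 − 148 = 2. The earlier pooled set in section 9.2 agrees: 30 + 110 − 138 = 2. So 2 of 10 in one cohort out of twelve were enrolled under Part I criteria.

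**2. What does Appendix 1 give a subject with no target lesions?** The nine rows of table D have these target-lesion entries:
- CR (three rows), PR, SD, not all evaluated, and progressive disease: seven rows that presuppose target lesions. The not-all-evaluated row (overall NE) describes target lesions that exist but were not all assessed.
- Any (two rows): both lead to progressive disease.

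Only progression is defined. Overall SD in table D requires SD of target lesions, so table D does not turn table B's non-target label into overall SD. Table B does allow CR of non-target lesions, but no row of table D carries it to an overall response. The immune-related table in Appendix 2 has the same gap.

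**3. The plan's design figures.** Inputs from Protocol 15.7: null rate 5%, alternative 20%, one-sided alpha 0.05, power 0.80, at least 1 of 10 to continue, at least 4 of 29 to succeed. With 19 subjects after stage 1, P(success) = Σ over x = 1 to 10 of P[Bin(10,p) = x] × P[Bin(19,p) ≥ 4 − x]. This gives 0.0468 at 5% and 0.8011 at 20%, so the stated design reproduces.

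**4. Bounds on the effect.** Let k be the number of the ten without target lesions. The documents do not give k; here it can be 0, 1 or 2. These are limiting cases, not estimates. They take the plan's 5% and 20% as the success rate for everyone else.

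*Such subjects never count as a success.* Replace 10 by 10 − k in the stage-1 term. Stage-1 pass is 1 − (1 − p)^(10 − k).

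| k | Stage-1 pass, p = 20% | Full design, p = 5% | Full design, p = 20% |
|---|---|---|---|
| 0 | 0.893 | 0.047 | 0.801 |
| 1 | 0.866 | 0.041 | 0.767 |
| 2 | 0.832 | 0.035 | 0.726 |

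*Such subjects are always scored SD.* Stage 1 is then passed automatically, and success needs at least 4 − k of the other 29 − k. At p = 5%:
- k = 1: 1 − (0.2378 + 0.3505 + 0.2490) = 0.163
- k = 2: 1 − (0.2503 + 0.3558) = 0.394

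Against the design value of 0.047, the direction and size depend entirely on an unstated scoring convention and an unknown k.

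**5. ORR denominator.** With x responders among the others, the reported rate is x/10 instead of x/(10 − k). At k = 2, one responder gives 10% instead of 12.5%, a ratio of 8/10. At k = 0 nothing changes.

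**The case against.** Most of the case against concerns consequences, and much of it stands.

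- **No affected subject is known.** Nothing in the documents says that any Part I subject, or either carried-over subject, lacked measurable disease. This stands.
- **The printed rules give no SD.** A reader might infer that non-target persistence opens the gate. Table D does not support that, because overall SD requires target-lesion SD. What remains is an ambiguity caused by table B's label.
- **Large worst-case figures mislead.** If both subjects lack target lesions and each has an assumed 10–30% chance of SD, the two alone would open the gate with probability 1 − 0.9² = 0.19 to 1 − 0.7² = 0.51. That has no source and ignores the other eight. At the same assumed rate those eight open it with probability 0.57 to 0.94, and all ten with 0.65 to 0.97, so the two add only 0.08 to 0.03. Two measurable subjects with the same rate would add exactly as much. Likewise, a claim that Part I ORR is understated by a fifth needs 6 of 30 without measurable disease (24/30 = 0.80). The documents give no such count, and the claim also assumes that CR is impossible for these subjects.
- **Appendix 1 may already bar them.** Read with criterion 7, it could be taken to govern carried-over subjects too. But 15.6 does not refer to it, and section 1.2 says subjects stay in the part they entered, so the sections need reconciling.
- **Appendix 1 is an excerpt.** It says so and points to the full guideline, which may cover this case. That does not settle what this plan's CBR counts.
- **The gate is permissive.** Section 15.7 says a cohort may be expanded, and section 4 allows a minimal signal not to be advanced. True, and this limits the harm.
- **Part I ORR is secondary and exploratory,** and both SAPs plan best response by target, non-target and overall. So the information needed is largely planned already, but the ORR denominator and CBR rule are still not fixed.

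**Conclusion.** The point holds as a minor one. Section 15.6 as written can place a subject who fails the Part II entry criterion into a cohort with a primary response outcome, and it was used for two of ten subjects in one cohort. The ORR denominator does not exclude subjects who cannot reach PR, and a non-progressing subject without target lesions has no overall response under table D.

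The effect lies between nil (k = 0) and, in that one cohort, the limiting cases above. Power falls from 0.801 to 0.726 if two such subjects can never count, or the false-positive chance rises from 0.047 to 0.394 if both are always scored SD. The documents support neither extreme as an expectation. They do not show that the gate was or would be opened wrongly, nor that Part I ORR is biased by any stated amount. The two subjects' baseline lesion records (target and non-target listing, Part I SAP listing 16.2.27) would settle k.

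**What to change.** - **Protocol 15.6:** add to the dose condition that a carried-over Part I subject had measurable disease at baseline, matching criterion 7 and Appendix 1. Reconcile this with the statement in section 1.2 that subjects do not move between parts.
- **Both SAPs:** compute ORR in efficacy evaluable subjects with measurable disease at baseline, and state how many subjects this removes.
- **Both SAPs:** report any non-target-only subjects separately (CR, neither CR nor progression, progression). State before analysis whether the middle category counts toward CBR. Either choice can be defended, but it should not be left to the table B label. Apply the same rule to the immune-related criteria.

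**Cost:** a few lines of wording, a slightly smaller ORR denominator, and at most two fewer or replaced subjects in the colorectal 0.3 mg/kg cohort. If all carried-over and Part I subjects had target lesions, no result changes.
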